9.2. Setting

All female patients treated with SC Peginterferon beta-1a therapy or IM Interferon beta-1a therapy who fulfill the inclusion criteria are eligible to participate in the study.

Patients registering in the PSP of the MSSC have to sign a privacy policy allowing the use of collected data for scientific purposes. This written consent covers the extract of data concerning the pregnancy reporting (retrospective part of the study).

All participants taking part in the prospective part of the study will be provided with a study specific patient information form and are informed by the MSSC of all pertinent aspects of the study. Written informed consent will be obtained from the participant (or legal representative) before the telephone interview takes part.

9.2.1. Selection Criteria

The patients will only be included in the study if they meet all of the following criteria:

Inclusion Criteria

1. Female patients of at least 18 years at time of informed consent
2. Diagnosed RRMS or CIS (CIS indication only applicable for interferon beta-1a)

CONFIDENTIAL

The information contained herein may not be used, disclosed, or published without the written consent of
Biogen MA Inc.

3. Exposure to either SC Peginterferon beta-1a therapy or an IM Interferon beta-1a therapy before or during pregnancy
4. Registered in the PSP of the MSSC and agreed in writing to the privacy policy of the registration form
5. Reported pregnancy data (pregnancy report and pregnancy outcome report) available at MSSC. Note: only pregnancy data (i.e. obtained until 15 October 2021) will be considered.

For the prospective part of the study:

6. Ability to understand the purpose of the study and provide signed and dated study-specific informed consent form (ICF)
7. Pregnancy outcome in the retrospectively collected data was a live birth

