8.3. Secondary Objectives

The secondary objectives of this study are applicable for a subpopulation of the above-mentioned population, i.e. for patients of whom data on a standardized questionnaire collected during a telephone interview is available. The secondary endpoints are as follows:

- To evaluate the impact of exposure to SC Peginterferon beta-1a or IM Interferon beta-1a before and during pregnancy on **child development** up to 48 months of age
- To assess the SC Peginterferon beta-1a or IM Interferon beta-1a **treatment behavior** for pregnant women or women becoming pregnant in daily real life
- To assess the other MS **treatment behavior** during/after pregnancy

CONFIDENTIAL

The information contained herein may not be used, disclosed, or published without the written consent of
Biogen MA Inc.

- To assess the use of certain concomitant medications (i.e. non-disease-modifying therapies) taken during pregnancy
- To evaluate the effect of SC Peginterferon beta-1a or IM Interferon beta-1a exposure before, during, and after pregnancy on MS **disease activity**
- To assess the effect of breastfeeding under SC Peginterferon beta-1a or IM Interferon beta-1a therapy on the MS disease activity
- To assess the benefit of exclusive breastfeeding versus complementary feeding on the MS disease activity in women breastfeeding under SC Peginterferon beta-1a or IM Interferon beta-1a therapy

CONFIDENTIAL

The information contained herein may not be used, disclosed, or published without the written consent of Biogen MA Inc.

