9.1.2. Secondary Endpoints

- Average weight, average length, and average head circumference of the children from birth to 48 months
- Number and proportion of abnormalities diagnosed during pediatric check-ups under statutory programs in Germany and reported in the standardized German pediatric check-up booklet “Kinderuntersuchungsheft” (data on check-ups 1-8 will be collected covering the first 46 - 48 months of life). Refer to Annex 3 for recommended timepoints and details on the examinations.
- Number and proportion of women discontinuing SC Peginterferon beta-1a or IM Interferon beta-1a therapy during pregnancy and time to discontinuation in relation to beginning of pregnancy

CONFIDENTIAL

The information contained herein may not be used, disclosed, or published without the written consent of Biogen MA Inc.

- Number and proportion of women starting SC Peginterferon beta-1a or IM Interferon beta-1a therapy during pregnancy and time to start in relation to beginning of pregnancy
- Number and proportion of women restarting SC Peginterferon beta-1a or IM Interferon beta-1a therapy after birth and time to restart in relation to birth
- Number and proportion of women starting another MS therapy during/after pregnancy and time to start in relation to birth
- Number and proportion of women using other therapies during pregnancy (categorized by Paracetamol, other therapies for the alleviation of FLS), folic acid, medication for depression, corticosteroids, adrenocorticotrophic hormone, other therapies)
- Number and proportion of MS relapses in women with SC Peginterferon beta-1a or IM Interferon beta-1a therapy before, during and after pregnancy
- Change of EDSS during and after pregnancy to EDSS before pregnancy
- Lactation: number of women breastfeeding under SC Peginterferon beta-1a or IM Interferon beta-1a therapy and duration of SC Peginterferon beta-1a or IM Interferon beta-1a exposed breastfeeding
- Time to first MS relapse after introduction of the first supplemental feedings in women with SC Peginterferon beta-1a or IM Interferon beta-1a therapy during lactation

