9.4.2. Prospective Data Capture

If the pregnancy report or the pregnancy outcome report is incomplete, i.e. the data above was not collected, the open questions will be addressed during a telephone interview performed by the MSSC and the new information will be entered into the MSSC database. No further assessments other than completion of the questionnaire are applicable for patients participating in the prospective study part. The patient questionnaire is completed at a single point of time during the telephone interview performed by the MSSC.

The patient questionnaire covers the following questions:

- Abnormalities diagnosed during pediatric check-ups under statutory programs as reported in the standardized German pediatric check-up booklet “Kinderuntersuchungsheft” (data on check-ups 1-8 will be collected covering the first 46-48 months of life)
- Pregnancy and family anamnesis
- Vitamin K prophylaxis
- Body weight, height, head circumference of the child as documented for check-ups 2-8.
- Lactation:
 - Exclusive breastfeeding and duration (1st week, 1 month, 2 months, 3 months, 5 months, 6 months, 7-9 months, 10-12 months, > 12 months) of breastfeeding
 - Supplemental feedings (starting month after birth)
- Other MS therapies (non-interferon beta-1a DMTs) during or after pregnancy and start relative to birth (during pregnancy, < 1 week after birth, after 1 week, after 2 weeks, after 3 weeks, after 4 weeks, after 6 weeks, after 2 months, after 3 months, after 4 months, after 5 months, after 6 months, after 7 months, after 8 months, after 9 months, after 10 months, after 1 months, after 12 months or later))
- Frequency of MS relapses in the year before pregnancy
- Time (1st trimester, 2nd trimester, 3rd trimester) and frequency of MS relapses during pregnancy

CONFIDENTIAL

The information contained herein may not be used, disclosed, or published without the written consent of Biogen MA Inc.

- Time (< 1st month, 1st – 2nd month, 3rd - 4th month, 5th - 6th month, 7th - 8th month, 9th - 10th month, 11th - 12th month, 13th - 14th month, 15th - 16th month, 17th - 18th month, > 18th months) and frequency of MS relapses after pregnancy/birth
- EDSS before, during and after pregnancy

The information collected by the MSSC will be stored in a secure database.

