16. ANNEX 3: ADDITIONAL INFORMATION

Flowchart

	MSSC database	Patient questionnaire
Prior to enrollment (i.e. generating data extract for pregnancy reporting data from MSSC database and obtaining written informed consent for prospective study part)		
Selecting eligible participants by checking Inclusion/Exclusion Criteria	X	X
Ensuring that written agreement on the privacy policy of the PSP registration form is available	X	---
Identification of missing data in MSSC database	X	---
Contacting eligible participants by phone, explaining background of the proposed study, the data collected, and the voluntary nature of study participation, obtaining oral consent for proceeding with the prospective study part	---	X
Provision of Patient Information and collection of written Informed Consent	---	X
After enrollment		
Date of Informed Consent	---	X
Patient's demographics: age, weight, height	X	---
Pregnancy outcome, type of delivery, complications	X	---
Pregnancy anamnesis	---	X
Data on the newborn child	X	X
Family anamnesis of child	---	X
Data on child development (as reported in the standardized German pediatric check-up booklet "Kinderuntersuchungsheft")	---	X
Breastfeeding practices	---	X
Interferon beta treatment history before, during and after pregnancy	X	---
Other MS medications during and after pregnancy	---	X
Concomitant medication during and after pregnancy	X	---
MS disease activity	---	X
Premature Study Termination (only applicable for prospective study part)	X	---

CONFIDENTIAL

The information contained herein may not be used, disclosed, or published without the written consent of Biogen MA Inc.

Health checks for children in Germany as reported in the standardized German pediatric check-up booklet “Kinderuntersuchungsheft”

Examination type	Age	Scope of examination
U1	After birth	Skin colour, breathing, muscle tone, reflexes, heartbeat, Vitamin K prophylaxis
Advanced newborn screening	1–3 days old	Blood test to check for metabolic disorders
Newborn hearing screening	1–3 days old	Exclusion of hearing impairments from a hearing loss of 35 dB
Cystic fibrosis screening	1–3 days old	Generally a blood sample taken during advanced newborn screening
Pulse oximetry screening	2 days old, by U2 at the latest	Measurement of the blood oxygen levels using a light sensor on the baby’s foot. Low oxygen levels can be a sign of congenital heart defects. Vitamin K prophylaxis

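### Other disease-modifying therapies are neither an eligibility condition nor recorded for every pregnancy, so some pregnancies exposed to them can be counted as interferon outcomes without being reliably identified

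*Protocol*

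**What the plan says.** **Eligibility.** Section 9.2.1 states that "The patients will only be included in the study if they meet all of the following criteria". The criterion on treatment reads "Exposure to either SC Peginterferon beta-1a therapy or an IM Interferon beta-1a therapy before or during pregnancy". No look-back period is given, no exclusion criteria are listed, and none of the seven criteria concerns other DMTs. Under 9.7.1.1 the primary analysis set is everyone who is eligible, and under 9.7 the two interferon products are pooled.

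**Where other DMTs are collected.** Section 9.4.2 lists as a questionnaire item "Other MS therapies (non-interferon beta-1a DMTs) during or after pregnancy and start relative to birth". Its response categories open with "start relative to birth (during pregnancy, < 1 week after birth, after 1 week" and then run on through the months after birth. In the Annex 3 flowchart, the row "Other MS medications during and after pregnancy" is ticked for the patient questionnaire and dashed out for the MSSC database. The related secondary endpoint in 9.1.2 is "Number and proportion of women starting another MS therapy during/after pregnancy and time to start in relation to birth".

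**Who is interviewed.** Beyond consent, the prospective part requires "Pregnancy outcome in the retrospectively collected data was a live birth".

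**What is extracted for every pregnancy.** Section 9.4.1 covers study-interferon use with its duration before, during and after pregnancy, and concomitant medication before and during pregnancy. No other DMT is named. Section 8.3 describes the concomitant-medication objective as "To assess the use of certain concomitant medications (i.e. non-disease-modifying therapies) taken during pregnancy". Section 9.6 says the MSSC database holds therapeutic history.

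**The concern.** The primary objective (8.2) is the impact of interferon exposure on pregnancy outcome. A pregnancy also exposed to a different DMT, at conception or later, does not inform that question cleanly. If it cannot be recognised, its outcome is added to the interferon proportions with nothing to warn the reader.

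The gap is uneven across outcomes. Ectopic pregnancies, spontaneous and elective abortions and stillbirths are all primary endpoints (9.1.1), and none of these women is interviewed. For losses and terminations, the only planned source on other DMTs is whatever happens to be in the concomitant-medication extract.

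This concerns what is collected. A statistical analysis plan could define extra columns, but it could not fill them with data that the protocol does not plan to extract.

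**Working it through.** **Inputs (protocol 9.5, mid-July 2020).** There are 202 peginterferon and 245 IM interferon pregnancy-with-outcome reports, 368 live births, and about 290 expected questionnaires at an 80% return. The abstract expects about 310. I assume one questionnaire per live-birth pregnancy.

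**1. The plan's own figure.** 0.80 × 368 = 294.4, which agrees with about 290. The abstract's 310 does not follow from 368, since 310 / 0.80 = 387.5. It may anticipate growth in the database.

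**2. Pregnancies not asked about other DMTs.**
- Total: 202 + 245 = 447.
- Not live births: 447 − 368 = 79, and 79 / 447 = 17.7%. None is asked.
- Live births without an interview: 368 − 290 = 78.
- Together: 79 + 78 = 157, and 157 / 447 = 35.1%.
- With 294 interviews: 447 − 294 = 153, or 34.2%.
- With 310 interviews on the same 447: 447 − 310 = 137, or 30.6%.

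**3. Three kinds of pregnancy that satisfy criterion 3.**
- *Stopped interferon, switched, and conceived on another DMT.* The extracted interferon dates should show that interferon ended before conception. Unless interferon is restarted in pregnancy, she fits none of the three primary subgroups in 9.7.2, but she does enter the overall proportions. The extract list does not ask for the other drug.
- *Conceived on interferon, and another DMT was added or substituted during pregnancy.* She can sit inside a primary subgroup. If she has a live birth and is interviewed, the item captures the other drug. After a loss or termination it does not.
- *Conceived on another DMT, and interferon was started during pregnancy.* She belongs to a prespecified primary subgroup. The questionnaire may elicit the earlier drug if it was still used in pregnancy, but there is no category for its start. After a loss it is not asked.

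**4. Scale, by assumption only.** The documents give no count of such pregnancies. Take an assumed share f of 1% to 10%, which is 4.5 to 44.7 of 447. Suppose, purely for illustration, that these carried the upper general-population rates quoted in 7.1.2 and the rest carried the registry rates.
- Spontaneous abortion: shift = f × (21 − 10.7) = 0.10 to 1.03 percentage points.
- Live births with anomalies: shift = f × (4.1 − 1.8) = 0.02 to 0.23 points.

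For comparison, approximate 95% half-widths at n = 447 are:
- 1.8%: 1.96 × √(0.018 × 0.982 / 447) = 1.2 points.
- 10.7%: 1.96 × √(0.107 × 0.893 / 447) = 2.9 points.

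On these assumptions the shifts are smaller than sampling error.

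**The case against.** The case on the other side is substantial, and much of it stands.

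- **Some of these pregnancies can be recognised.** Interferon dates are extracted for everyone, so a woman who left interferon before conception is visible and falls outside the primary subgroups. A reader might infer that contaminated pregnancies can never be separated at analysis. The documents do not support that. The extract does not, however, plan to say whether she was then untreated or on another DMT.
- **Concomitant medication is extracted for every pregnancy and reaches back before conception.** The restriction to non-disease-modifying drugs belongs to one secondary objective and does not define the database field, so some DMTs may be recorded there. This stands as a possibility. But the extract list names no DMT, the protocol lists other MS therapies separately, and the flowchart dashes them out for the database.
- **The questionnaire item would elicit a DMT still used in pregnancy.** This is correct. What is lost is when it began. The questionnaire itself is not shown, only a list of its contents.
- **Not all adverse outcomes are missed.** A reader might infer that the information is absent wherever an adverse outcome occurs. It is not: mothers of live-born children with anomalies, and of live preterm births, can be interviewed. The complete gap is confined to pregnancies that did not end in a live birth.
- **Such pregnancies may be rare.** Sections 9.1 and 9.5 describe women treated with, or under, interferon, and the support programme serves users of these two products. The secondary endpoint on starting another therapy is mostly about the period after birth and is no evidence of conception on another drug. This stands.
- **The study is descriptive and admits that it has no comparator (9.9).** True, but 9.9 does not mention other DMTs, and the primary objective is still worded as the impact of interferon.

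**Conclusion.** The point holds as a gap in data capture. Eligibility sets no condition on other DMTs, and the only planned item on them misses all 79 pregnancies that were not live births and about 78 further live births: 157 of 447, or 35%. The figure is about 31% if 310 questionnaires are completed against the same 447. For a DMT started before conception, the item has no start category for anyone. Pregnancies with another DMT at conception or later can therefore be counted as interferon outcomes without being reliably identified, most of all among losses and terminations.

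The 35% is the share not asked. A reader might take it as the share contaminated, or infer that the reported proportions are biased by a known amount. Neither follows, because the number of such pregnancies is unknown and may be small, and the shifts worked out above rest entirely on assumed values. The change is worth making because it is cheap and bears directly on the primary objective.

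**What to change.** 1. In 9.4.1 and the Annex 3 flowchart, add other-DMT use to the MSSC extract for every pregnancy: product, and start and stop relative to conception. Draw it from the therapeutic history that 9.6 says is already held.
2. In the 9.4.2 questionnaire item, add a category for therapy started before pregnancy, and a stop date.
3. Report the primary endpoint overall and in three further columns: no other DMT from the last interferon dose before conception to the outcome; another DMT in that period; status unknown. For women whose only interferon exposure began in pregnancy, state separately where that period starts.

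The cost is a few extract fields, one questionnaire category with a date, and a smaller denominator for the column without other DMTs. No additional patients or contacts are needed. If the therapeutic history proves incomplete, the unknown column will show it.

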7.1.2. Clinical Experience with Interferon Beta

Available data on the safety of interferons during pregnancy and breastfeeding was limited, as interventional clinical trials generally exclude pregnant patients.

Two large prospective cohort studies provide evidence for safety data of women in a child-bearing age with MS under interferon beta exposure:

- A European Interferon beta Pregnancy Registry, a prospective observational collection of information on women with MS exposed to interferon beta during pregnancy, was established to address the lack of evidence. Using spontaneous and solicited reports, the registry collected data from 26 countries of the European Economic Area. Cumulative data from 2447 pregnancies with 948 reported outcomes were collected from April 2009 to June 2017 in the European Interferon beta Pregnancy Registry.

An analysis from the registry showed that the prevalence of spontaneous abortions (10.7% vs up to 21%) and live births with congenital anomalies (1.8% vs 2.1 - 4.1%) were comparable with the numbers reported in the general population [Hellwig 2020].

- A population-based cohort study was conducted leveraging healthcare register data from two Nordic countries (Finland and Sweden). In this Nordic register cohort study, the prevalence of infant outcomes after birth have been analyzed (3054 pregnancy events with known pregnancy outcomes) including interferon beta exposed women (n= 814) compared to interferon beta unexposed women (n= 1831).

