9. RESEARCH METHODS

9.1. Study Design

This non-interventional, voluntary PASS is designed as a single-center open-label survey.

Spontaneously reported safety data are available for pregnant MS patients treated with SC interferon beta therapy or an IM interferon beta therapy in the German PSP of the MSSC.

In addition, a prospective data collection is performed by completing a standardized questionnaire while interviewing MS patients who reported a “live birth” and for which a signed ICF is available.

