9.4. Data Sources

9.4.1. Retrospective Data Capture

Main data source for the retrospective data capture is the MSSC database, i.e. the entered pregnancy report (to be completed as soon as pregnancy becomes known) and pregnancy outcomes report (to be completed after completion of pregnancy).

The following data is extracted from the MSSC database:

- Demographic data (age, height, weight)
- SC Peginterferon beta-1a or IM Interferon beta-1a use, including treatment duration, prior to, during and after pregnancy
- Concomitant medication prior to and during pregnancy
- Pregnancy outcome (live birth without defect, live birth with defects, ectopic pregnancy, spontaneous abortion, elective termination of pregnancy, preterm birth, stillbirth), including gestation week and description of abnormalities of the fetus, reason for termination, diagnostics, etc.
- Complications during pregnancy

CONFIDENTIAL

The information contained herein may not be used, disclosed, or published without the written consent of Biogen MA Inc.

- Type of delivery (vaginal delivery: spontaneous, induced, instrumentally supported; Caesarean section: elective, medically indicated), complications during delivery or reasons for an intervention
- Placenta normal/abnormal
- Data on newborn (sex, weight, height, head circumference, Apgar 1 minute, Apgar 5 minutes, Apgar 10 minutes)

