9.5. Study Size

Since this is an exploratory study and no formal hypothesis-testing will be carried out, there is no formal sample size calculation. The sample size of this study depends on how many patients are eligible to participate in this observation and will agree to provide data for the questionnaire.

As of mid-July 2020, there were n = 202 pregnancy and pregnancy outcome reports for 184 female patients under SC Peginterferon beta-1a and n = 245 pregnancy and pregnancy outcome reports for 199 female patients treated with IM Interferon beta-1a in the MSSC database. The outcome of 368 pregnancies was a live birth, hence qualify for the prospective study part. About 290 patient questionnaires are expected to be completed during the telephone interview (80% return rate estimated). This number might increase until 15th October 2020 - the cut-off point for data collection.

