9.6. Data Management

MS Service-Center database:

The Biogen MS Service-Center provides medical information to German MS patients on request. Furthermore, it offers enrollment to a patient support program for SC Peginterferon beta-1a and IM Interferon beta-1a patients including injection handling training and individual adherence coaching from a personal coach upon medical need. Services have been provided since October 2014 from Audimedes GmbH, certified according to ISO 9001:2015 criteria. Compliance with these criteria is audited annually by an external certified audit organization. Database includes data of about 45,000 patients with MS.

From 2014 until December 2019 3, 615 patients under IM Interferon beta-1a treatment and 7,529 patients under SC Peginterferon beta-1a treatment have been enrolled to the patient support program. In the database, demographics and therapeutic history including adverse events, product complaints and pregnancy reports are captured in real time. All personnel dealing with the patient information and database undergo regular training to ensure quality of information, communication skills and quality of data in the database. All data is pseudonymized and pooled for this analysis.

Study database:

Data collection for the retrospective study part will be performed by extracting the relevant data from the existing MSSC database and importing it into an electronic PDF (ePDF) by a CRO. During the telephone interview, missing data will be completed directly in the ePDF, if appropriate. After the CRO has received all completed ePDFs, all

CONFIDENTIAL

The information contained herein may not be used, disclosed, or published without the written consent of
Biogen MA Inc.

data will be exported and used for analysis by the CRO as well as for updating the MSSC database (Audimedex GmbH).

All relevant data for the prospective study part is documented on standardized patient questionnaires provided as ePDF. The MSSC personnel documents the results of the telephone interview directly in the ePDF and after completion, the ePDF is transferred to the CRO to export and analyze the data together with the retrospective data.

Personal data of patients are gathered, stored and processed exclusively in a pseudonymous form according to national data protection laws.

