10.7 Does the plan describe methods for handling missing data?				9.7
10.8 Are relevant sensitivity analyses described?				

Comments:

PAS study with one pooled treatment

Section 11: Data management and quality control	Yes	No	N/A	Section Number
11.1 Does the protocol provide information on data storage? (e.g. software and IT environment, database maintenance and anti-fraud protection, archiving)				9.6
11.2 Are methods of quality assurance described?				9.6
11.3 Is there a system in place for independent review of study results?				9.8

CONFIDENTIAL

The information contained herein may not be used, disclosed, or published without the written consent of Biogen MA Inc.

Comments:

--

Section 12: Limitations	Yes	No	N/A	Section Number
12.1 Does the protocol discuss the impact on the study results of: 12.1.1 Selection bias? 12.1.2 Information bias? 12.1.3 Residual/unmeasured confounding? (e.g. anticipated direction and magnitude of such biases, validation sub-study, use of validation and external data, analytical methods)				9.9
				
				
12.2 Does the protocol discuss study feasibility? (e.g. study size, anticipated exposure uptake, duration of follow-up in a cohort study, patient recruitment, precision of the estimates)				9.2.3.1

Comments:

--

Section 13: Ethical/data protection issues	Yes	No	N/A	Section Number
13.1 Have requirements of Ethics Committee/ Institutional Review Board been described?				10.1
13.2 Has any outcome of an ethical review procedure been addressed?				10.1

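### Inclusion conditional on an outcome report, crude proportions and no record of report timing leave the primary outcome percentages open to selection, and spontaneous abortion also to delayed entry; Section 9.9 does not discuss it

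*Protocol*

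**What the plan says.** Protocol Section 9.2.1, criterion 5, admits a pregnancy only with "Reported pregnancy data (pregnancy report and pregnancy outcome report) available at MSSC". Section 9.7.1.1 builds the primary analysis set from the eligible patients. Section 9.1.1 defines the primary endpoints as numbers and proportions of each outcome. Section 9.7 sets the denominator at all pregnancies in the group unless otherwise indicated.

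On the source, Section 9.1 states "Spontaneously reported safety data are available for pregnant MS patients", and Section 9.4.1 describes "the entered pregnancy report (to be completed as soon as pregnancy becomes known", followed by an outcome report once the pregnancy has ended. The outcome item is extracted "including gestation week and description of abnormalities of the fetus, reason for termination, diagnostics, etc". The date or gestational week of the first report is not among the listed items. The primary-endpoint subgroups in Section 9.7.2 split by interferon use only.

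Section 9.9 names the missing comparator and missing or implausible values as limitations. In Annex 2, checklist item "12.1.1 Selection bias" is ticked Yes with a pointer to Section 9.9. Item 7.2 (selection bias addressed) is marked not applicable, and item 10.8 (sensitivity analyses) is marked No.

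**The concern.** Three mechanisms act on the planned percentages.

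- **Delayed entry.** A woman who first reports at week 10 could not have been counted with a loss at week 7. A crude percentage treats her as observed from conception, so early losses are under-represented. This acts mainly on spontaneous abortion.
- **Selective outcome reporting.** A reported pregnancy without an outcome report is in neither numerator nor denominator. If such pregnancies ended differently from the rest, every primary percentage shifts. The Missing row promised in Section 9.7 does not reveal them, because they are removed before tabulation.
- **Outcome-driven reporting.** If some women report because of a loss or an abnormal finding, spontaneous abortion and anomaly percentages rise. Nothing in the protocol excludes or separates such reports.

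The primary objective concerns the impact of exposure on pregnancy outcome, and the title-page research question says the study is to supplement the interferon beta registries. Section 7.1.2 sets registry results beside general-population figures (spontaneous abortion 10.7% against up to 21%; anomalies 1.8% against 2.1-4.1%). Readers are likely to place the new percentages next to those.

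**Working it through.** **1. The plan's own figures (Section 9.5).** The section gives "n = 202 pregnancy and pregnancy outcome reports for 184 female patients under SC Peginterferon beta-1a" and 245 pregnancies in 199 women on the IM product.
- Pregnancies: 202 + 245 = 447. Women: 184 + 199 = 383.
- Live births: 368/447 = 82.3%. Other outcomes: 79/447 = 17.7%, not broken down by type.
- Questionnaires: 0.80 × 368 = 294.4, which agrees with the stated figure of about 290.

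All 447 have a known outcome by construction. The number of reported pregnancies without one is not given.

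**2. Delayed entry (assumed inputs).** Let T be the true loss risk from week 5, with losses at week 5 plus an exponential lag of mean m, truncated at week 22. The share of losses occurring at or after entry week e is

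S(e) = [exp(−(e−5)/m) − exp(−17/m)] / [1 − exp(−17/m)],

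and the crude risk among pregnancies first reported at week e is

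T·S(e) / {1 − T·[1 − S(e)]}.

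With T = 15%:
- e = 8, m = 3: S = 0.366, so 0.0549/0.905 = 6.1%.
- e = 8, m = 5: S = 0.533, so 0.0800/0.930 = 8.6%.
- e = 10: 3.2% to 5.8%.
- e = 12: 1.6% to 3.7%.

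A different assumed curve (weekly losses over weeks 5 to 21 falling geometrically with a half-life of 2 or 3 weeks) gives 11.1-12.2% at week 6, 5.8-8.0% at week 8 and 1.5-3.1% at week 12.

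**3. Opposing pull (assumed inputs).** Take the week-8 values of 5.8% and 8.0% from the second curve. Suppose 30% of reports came after the outcome, with 15% to 50% of those being losses.
- Low end: 0.7 × 5.8 + 0.3 × 15 = 8.6%.
- High end: 0.7 × 8.0 + 0.3 × 50 = 20.6%.

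The pooled figure can fall on either side of the assumed true 15%.

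**4. Outcome-conditional inclusion (assumed inputs).** Let p = 10.7% be the spontaneous abortion risk among pregnancies with an outcome (the registry figure in Section 7.1.2, borrowed for scale), f the share with an outcome, and RR the relative risk in the remainder. The all-pregnancy risk is p·[f + RR·(1 − f)]. For RR from 0.5 to 3:
- f = 90%: 10.2% to 12.8%.
- f = 60%: 8.6% to 19.3%.
- f = 38.7%: 7.4% to 23.8%.

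The last value of f comes from the registry in Section 7.1.2: "Cumulative data from 2447 pregnancies with 948 reported outcomes", that is 948/2447 = 38.7%. At that share, 447 outcomes would correspond to 447 × 2447/948 = 1,154 reports. Nothing shows that this share applies here.

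**5. Scale.** The exact 95% interval for 48/447 (10.7%) is 8.0% to 14.0%. Under several of the scenarios above, the shift is as large as or larger than sampling error.

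**6. Checklist against text.** Item 12.1.1 claims a discussion of selection bias in Section 9.9, and that section contains none. This needs no assumption.

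**The case against.** The best defence is that the protocol describes two sequential forms, the first made when pregnancy becomes known, and Section 9.6 says "pregnancy reports are captured in real time". The study is exploratory, tests nothing and declares itself non-comparative. Section 9.7 leaves analysis detail to a SAP, where attrition counts or a timing split could be added.

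Much of this stands. A reader might infer that reports made before and after the outcome was known are in fact pooled. No section says that any report followed a known outcome; the text only fails to exclude or separate such reports. A reader might also attribute delayed-entry bias to the anomaly percentage. That mechanism acts mainly on spontaneous abortion; for anomalies the exposure is to selective or post-diagnosis reporting, and no size is given here. The illustrative percentages describe hypothetical cohorts entering at a single week with every earlier loss missed, so they are not a forecast of the planned estimate. The general-population ranges belong to the registry's analysis, and this protocol plans no external comparison.

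The SAP argument stands only in part. A SAP may add tables, but eligibility and the extraction list are fixed in the protocol. Without report timing, neither the split nor a delayed-entry estimate can be made. The telephone completion in Section 9.4.2 does not recover excluded pregnancies, because criterion 7 limits the interview to recorded live births.

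**Conclusion.** The point holds as an uncontrolled and undiscussed vulnerability. It is not a demonstrated bias of known sign. As written, the crude spontaneous abortion proportion is open to delayed entry, and all primary proportions are open to selective or outcome-driven reporting. Late entry lowers the spontaneous abortion percentage, outcome-driven reporting can raise it, and missing outcomes can move it either way. The protocol gives neither the number of reports without an outcome nor the week of first report, so the net effect cannot be determined. The ranges above rest on an assumed 15% risk, assumed loss curves and assumed shares. The mismatch between Section 9.9 and Annex 2 is certain from the text.

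**What to change.** 1. Report how many otherwise eligible pregnancy reports up to the cut-off lack an outcome report, by exposure subgroup.
2. Add to the Section 9.4.1 extraction list the date of the first report, and the gestational week at report where it is stored or can be derived.
3. Show the primary proportions separately for pregnancies reported before and after the outcome or an abnormal prenatal finding was known, alongside the pooled figures.
4. For spontaneous abortion only, add a cumulative incidence to week 22 with delayed entry at the gestational week of report, treating elective abortion and ectopic pregnancy as competing events. This does not repair the loss of pregnancies without an outcome report, so item 1 is still needed.
5. Discuss selection bias in Section 9.9 and correct checklist items 7.2 and 12.1.1.

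The cost is protocol wording and a slightly wider extraction. Real-time capture suggests that report dates exist, but whether gestational week at report is stored is not stated. No new patient contact is needed for stored items. Estimates restricted to reports made before the outcome will rest on fewer than the 447 pregnancies, and the early-week risk sets may be small.
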